Implant	Day 0	Day 0
1 Month	Day 30	1 – 90 days
6 Months	Day 183	91 – 304 days
12 Months	Day 365	305 – 548 days
2 Year	Day 731	549 – 913 days
3 Year	Day 1096	914 – 1278 days
4 Year	Day 1461	1279 – 1644 days
5 Year	Day 1826	1645 – 2009 days

If there are two or more assessments in the same time window, then the assessment closest to the target day will be used in the analysis of event rate at a given time point.

In addition to endpoints, summaries of subject disposition, demographics, baseline characteristics, and subject accountability will be provided.

During statistical analysis, imputation of missing data will not be performed except for data related to the onset date of an adverse event or a death. In cases where the onset date of an event or a death is incomplete and unresolvable via data query, the 15th day of the known month or July 1st of the known year will be used.

Statistical analyses for this study will be performed using the Statistical Analysis System (SAS) for Windows (Version 9.1 or higher) or other widely-accepted statistical or graphical software.

Analysis for the regulatory submission:

For the primary endpoint, a one-sided 95% confidence interval based on binomial distribution will be constructed in addition to event count and frequency. Subset analysis will be performed by-sex for the primary endpoints descriptively and reviewed for clinical significant difference. All analysis will be performed on the intent-to-treat analysis set, which includes all enrolled subjects. Subjects will be considered as enrolled in the study as described in section F.1.

The analysis for the regulatory submission will take place when 40 subjects have been implanted with the study device for at least 30 days except that a subject expires early.² Endpoints as defined in Section C.2 will be analyzed for these 40 enrolled subjects.

Interim Analysis:

No interim analysis is planned prior to the regulatory submission.

Annual Report:

An annual report will be provided including all enrolled subjects at the time of reporting if required per local law and regulations.

H.2 Publication Policy

Publications and presentations referring to this clinical study will be coordinated by Medtronic to allow the use of all available data. The following publication policy will have to be adhered to by all participating investigational sites:

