3.1. Treatment and Subject Enrollment

The study population will include those subjects who are appropriate candidates for endovascular repair of infrarenal abdominal aortic or aortoiliac aneurysms, and who meet the Inclusion/Exclusion criteria (defined in the Clinical Investigation Plan Section D).

For subjects that are treated with the bifurcated stent graft minimal 3 pieces will be implanted in the target segment; one bifurcated stent graft component and 2 limb stent graft components. For subjects that are treated with the AUI component approximately 2 pieces will be implanted in the

target segment; the AUI stent graft component and one limb stent component. Additional stent graft extensions might be needed to cover the complete target lesion length.

A sample of 40 subjects will be treated and evaluated at the 30-day primary safety endpoint. Data from these 40 subjects will be analyzed and used to support regulatory approval. All subjects treated will continue to be followed under this investigational protocol beyond the 30-day primary endpoint until 5 years post-implantation.

Subjects will have required follow-up evaluations at the following time points:

- 1 month following the index procedure
- 6 months following the index procedure
- 12 months following the index procedure
- Annually thereafter, until 5 years post index procedure

In addition to the 40 subjects to support regulatory approval, approximately 30 additional subjects may be treated to support geography-specific regulatory requirements. For these subjects, all inclusion/exclusion criteria, study methods, follow-up schedule and data-collected will be identical to the first 40 subjects.

Approximately 10 sites will participate in the clinical study. For the initial 40 subjects to be analyzed, no more than 20% (i.e. 8 subjects) will be treated from a single investigational site. Enrollment will be halted at sites that reach the 20% enrollment cap. Following enrollment of the first 40 subjects, up to approximately 30 additional subjects can be enrolled and a site where enrollment has been halted may resume enrolling. For the total cohort of 70 subjects again no more than 20% of subjects will be treated from a single investigational site which results in a maximum enrollment per site of 14 subjects.

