The total enrollment period is not expected to exceed 12 months. All treated subjects will be followed until 5 years post-implantation. Thus total study duration from first subject treated to final subject exit could approach 6 years.

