4.2. Subset

Subset analysis will be performed by-sex for the primary endpoints descriptively and reviewed for clinical significant difference.

5. Endpoints

Primary Safety Endpoint

The primary safety endpoint is defined as the proportion of subjects experiencing a MAE within 30 days post-implantation. MAEs include the occurrence of any of the following events:

- All-cause mortality
- Bowel ischemia
- Myocardial infarction
- Paraplegia
- Procedural blood loss ≥ 1000 cc
- Renal failure
- Respiratory failure
- Stroke

Primary Effectiveness Endpoint

Technical success at the index procedure (as assessed intra-operatively) is defined as successful delivery and deployment of the Endurant Evo AAA Stent graft system in the planned location and with no unintentional coverage of both internal iliac arteries or any visceral aortic branches and with successful removal of the delivery system.

Secondary Endpoints

- All cause-mortality within 30, 183, and 365 days
- Aneurysm-related mortality within 30, 183, and 365 days
- Secondary procedures to correct Type I and III endoleaks within 30, 183 and 365 days
- Secondary endovascular procedures within 30, 183 and 365 days
- Serious adverse events within 30, 183 and 365 days
- Aneurysm rupture within 30, 183 and 365 days
- Conversion to open surgery within 30, 183 and 365 days
- Major adverse events within 183 and 365 days
- Stent graft migration at 12-month follow-up visit (as compared to 1-month imaging)
- Aneurysm expansion > 5 mm at 12-month follow-up visit (as compared to 1-month imaging)
- All endoleaks based on imaging findings at 1- month, 6-month and 12-month visits
- Stent graft occlusion based on imaging findings through 6 months and 12 months
- Device deficiencies based on imaging findings through 6 months and 12- months

Secondary endpoints will be assessed at annual follow-up visits until 5 years post-implantation.

Additional Observations

The following acute procedural observations and clinical utility measures will be reported:

- Mean duration (min) of procedure (time between initial skin access to final skin closure)
- Proportion of subjects who underwent general/local/epidural/spinal anesthesia
- Proportion of subjects who underwent unilateral/bilateral percutaneous access
- Proportion of subjects requiring blood transfusions, excluding cell saver
- Mean volume (cc) of estimated blood loss
- Mean duration (min) of radiation exposure
- Radiation exposure (mGy)

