8.4. Analysis of the Primary Endpoints

For the primary endpoint, a one-sided 95% confidence interval based on binomial distribution will be constructed in addition to event count and frequency.

The analysis for the regulatory submission will take place when 40 subjects have been implanted with the study device for at least 30 days except that a subject expires early. Endpoints as defined in Section 5 will be analyzed for these 40 ITT subjects.

MAE Rate Calculation:

All MAEs will be adjudicated by the Clinical Event Committee (CEC) per protocol except for the procedural blood loss ≥ 1000 cc, which will be site reported at the index procedure. MAE rate will be calculated as follows (Table 2):

Table 2: MAE Rate Calculation:

MAE rate = $m/(m + k)$	Within 30 Days	Within 183 Days	Within 365 Days
$m = \text{No. of Subjects Who Had MAE(s)}$	No. of subjects who had at least one MAE with onset day from Day 0 to Day 30, inclusive.	No. of subjects who had at least one MAE with onset day from Day 31 to Day 183, inclusive.	No. of subjects who had at least one MAE with onset day from Day 184 to Day 365, inclusive.
$k = \text{No. of Subjects Who Had No MAE}$	No. of subjects who have been in study for at least 1 day and without an MAE.	No. of subjects who have been in study for at least 91 days and without an MAE.	No. of subjects who have been in study for at least 305 days and without an MAE.

If a subject is early terminated from the study, the last day that the subject has been seen will be the duration in study, which can be the day of last follow-up, last imaging taken, an AE reported, or withdrawal from the study. If a subject is still in the study, the duration in study will be the time from index procedure to the cut off day that the database is locked or data snapshot is taken.

Imaging based Event Rate Calculation:

Imaging assessment will be performed by site as well as the core lab. Assessments from the core lab will be analyzed separately from those by site. Imaging based event rate will be calculated using statistical analysis windows as follows (Table 3):

Table 3: Imaging based Event Rate Calculation:

Event rate = m/n	At 1 Month	At 6 Months	At 12 Months
$m = \text{No. of Subjects Who Had Event(s)}$	No. of subjects who had an event with scan day within the 1-month window.	No. of subjects who had an event with scan day within the 6-month window.	No. of subjects who had an event with scan day within the 12-month window.

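### The submission analysis is triggered at 30 days but told to cover every endpoint; at that cut the 365-day and 12-month proportions are undefined, 100% or inflated, and no later endpoint analysis is dated

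*SAP*

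**What the plan says.** **Trigger and scope.** SAP 8.4: "The analysis for the regulatory submission will take place when 40 subjects have been implanted with the study device for at least 30 days", with an exception for early death. The scope follows: "Endpoints as defined in Section 5 will be analyzed for these 40 ITT subjects". Protocol H.1 has the same trigger and says: "Endpoints as defined in Section C.2 will be analyzed for these 40 enrolled subjects".

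**What that scope contains.** SAP Section 5 lists "Major adverse events within 183 and 365 days"; mortality, secondary procedures, serious adverse events, rupture and conversion to 365 days; migration and expansion at 12 months; and endoleak, occlusion and device deficiency at 6 and 12 months. It adds: "Secondary endpoints will be assessed at annual follow-up visits until 5 years post-implantation".

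**Enrolment.** SAP 3.1: "The total enrollment period is not expected to exceed 12 months". The first 40 subjects are planned; about 30 more are optional. The current protocol records that enrolment ended at 69.

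**Formulas.** Table 2 defines the rate as m/(m+k).
- 183-day column: m counts onsets on Days 31 to 183; k needs at least 91 days in study.
- 365-day column: m counts onsets on Days 184 to 365; k is "No. of subjects who have been in study for at least 305 days and without an MAE".

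For ongoing subjects, time in study runs to database lock or snapshot. SAP 8.5 applies Table 2 to mortality, secondary procedures, serious adverse events, conversion and rupture. In Table 3, the Through 12 Months column counts an event seen in the 1-, 6- or 12-month window, but an event-free subject only with a readable 12-month image.

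**Other reporting.** SAP Section 7 plans no interim analysis before submission. Protocol H.1 provides an annual report where local law requires it. The opening of Section H and Tables I-1 and I-2 refer to a final clinical study report, without an analysis date or endpoint list.

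**The concern.** The trigger suits the 30-day endpoint and the scope does not. A programmer who follows SAP 8.4 literally must fill 183-day, 365-day and 12-month columns from subjects of whom the last has 30 days of follow-up.

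Tables 2 and 3 do not degrade gracefully on immature data. An event enters the numerator and the denominator on the day it happens. A subject without an event enters the denominator only after a waiting period. At an early cut the subjects still waiting are dropped, while any of them with an event are kept. The submission could then carry 12-month rates with no meaning, and no dated analysis follows to replace them. This matters because device deficiencies are among the affected endpoints, and the protocol gives device deficiencies as the reason enrolment was terminated.

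**Working it through.** **1. The plan's own figure.** SAP 3.2 states a margin below 10% for 2 MAEs in 40. The exact one-sided 95% upper limit is beta.ppf(0.95, 3, 38) = 14.9%, and 14.9% − 5% = 9.9%. It reproduces. It concerns the 30-day rate only; nothing comparable supports the later endpoints at this cut.

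**2. Follow-up at the trigger.** Cut = entry day of the 40th subject + 30, with the first subject at Day 0. The accrual patterns are assumptions.
- 70 evenly over 365 days: the 40th enters at 39/69 × 365 = 206.3, so the cut is Day 236.3. Entries are 365/69 = 5.29 days apart.
- 40 only, evenly over 365 days: cut at Day 395, entries 365/39 = 9.36 days apart.
- 40 only, accrual rising linearly: entry of subject i = 365 × √((i−1)/39), cut at Day 395.

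| Pattern | ≥91 days | ≥184 days | ≥305 days | ≥365 days |
|---|---|---|---|---|
| 70 evenly in 12 months | 28 | 10 | 0 | 0 |
| 40 only, evenly in 12 months | 33 | 23 | 10 | 4 |
| 40 only, rising in 12 months | 28 | 14 | 3 | 1 |

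Faster even accrual of 70 also gives 0 at Day 305. Someone reaches Day 305 by the trigger only if the 40th subject enters on Day 275 or later (305 − 30). In the first pattern, a lock delayed by 305 − 236.3 = 69 days does the same.

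**3. Table 2, 365-day column.**
- k = 0 (first pattern): 0/0 if no onset falls on or after Day 184, otherwise m/m = 100%.
- k = 10 (second pattern): one event in a subject with 184 to 304 days of follow-up gives 1/(1+10) = 9.1%. Yet 23 subjects had entered that interval (1/23 = 4.3%), of 40 in all (1/40 = 2.5%).
- Expected value, second pattern, events spread evenly over Days 184 to 365: the observed fractions of that interval sum to 13.43 over the 40 subjects. With an assumed true interval risk of 5%, m = 13.43 × 0.05 = 0.67 and k = 9.55, so the rate is 0.67/10.22 = 6.6%. Assumed risks of 2.5% and 10% give 3.3% and 12.9%.

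**4. Table 2, 183-day column.** First pattern: one event in a subject with under 91 days gives 1/(1+28) = 3.4%, against 1/40 = 2.5%. A second feature works the other way: k accepts subjects from Day 91 as event-free to Day 183. With a 5% true risk, events spread evenly give an expected 1.25/(1.25+26.86) = 4.5%. If events are concentrated early (cumulative share 1 − (1 − g)³, where g is the elapsed fraction of Days 31 to 183), it is 1.61/(1.61+26.65) = 5.7%. The upward push is real, but the net direction depends on event timing.

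**5. Table 3.** With no image in the 12-month window (Days 305 to 548), the At 12 Months column is 0/0. The Through 12 Months column has n = m, so one event in the 1- or 6-month window gives 100%.

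**The case against.** **The cut is meant for 30 days.** Protocol C.5 and SAP 3.1 describe the 40 as evaluated at the 30-day safety endpoint, and the scope sentence sits under the primary-endpoint heading. Many secondary endpoints have 30-day or 1-month versions available then, and the table shells are in a separate document. This is probably the intent, but both documents name the whole endpoint section and neither restricts it.

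**Follow-up is not known.** A reader might infer that no subject will have reached the 12-month window. The documents do not support that: 12 months is a ceiling, the extra 30 are optional, follow-up runs to lock, and actual entry dates are not given. This stands, and it is why a range is reported.

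**Not every estimate fails.** Kaplan-Meier mortality remains defined up to last follow-up. The failure belongs to the Table 2 and Table 3 proportions.

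**Later reporting is not excluded.** A reader might infer that nothing follows this cut. A final report is foreseen, H.1 defines the analysis set as all enrolled subjects, and its footnote gives 69. What is missing is a trigger and an endpoint list.

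**Two further readings go too far.** Two events over 2 + 10 would give 17%, but only with a cumulative numerator; Table 2 counts Day 184 to 365 onsets alone. A reader might also say that this cut hides late structural failure. The protocol gives no timing for the device deficiencies that ended enrolment, and their detection through core-lab reading, immediate reporting and the DMC does not depend on this analysis.

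**Conclusion.** The point holds. The trigger and scope conflict on the face of SAP 8.4 and Protocol H.1, whatever the accrual, and no later endpoint analysis is dated. The size depends on accrual: 0 of 40 subjects past Day 305 if 70 enter evenly in 12 months, and about 3 to 10 of 40 if only 40 enrol over 12 months, assuming prompt lock. The 365-day and 12-month proportions are then 0/0, 100% or inflated, with 9.1% from a single event as the example at the favourable end. The 183-day rates carry the same upward push, smaller and, when events are spread evenly, more than offset by the 91-day rule. The documents do not say whether the 40-subject analysis has been run. If it has, its 183- and 365-day figures need an immaturity label and the later analyses still need dates.

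**What to change.** In SAP 8.4 and Protocol H.1:

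1. Limit the 40-subject cut to technical success, 30-day events and 1-month imaging.
2. Report any event rate beyond 30 days at that cut by Kaplan-Meier or cumulative incidence with numbers at risk, not m/(m+k).
3. Add a dated analysis of the 183- and 365-day and 6- and 12-month endpoints on all 69 enrolled subjects, once each has passed Day 548 or has exited. Day 548 closes the 12-month analysis window in SAP Table 1 and Protocol Table H-1. Cutting when the visit window closes (Day 421, Protocol Table F-1) could lose eligible images from Days 422 to 548.
4. Add a final analysis of all 69 after the 5-year analysis window (Day 2009) or exit.

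The cost is wording in two sections; no new data are needed. The downside is that the first report withholds later endpoints until they are mature.

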PET	Polyethylene terephthalate
PMA	Premarket Approval
OD	Outer Diameter
SADE	Serious Adverse Device Effect
SAE	Serious Adverse Event
SOP	Standard operating procedure
USADE	Unanticipated Serious Adverse Device Effect
WBC	White Blood Cell

L.2 Definitions

Major Adverse Events (MAEs)	Definition
All-Cause Mortality	Death from any cause.
Bowel Ischemia	Bloody diarrhea with confirmation via colonoscopy of ischemia or the operative or postmortem demonstration of ischemic changes in the large or small intestine and requires surgical intervention.
Myocardial Infarction	Evidenced on 2 of the 3 following conditions: new clinical symptoms suggesting MI, changes on ECG consistent with MI, and elevated CK > 2 times the upper normal limit (per the normal ranges of the institution).
Paraplegia	Complete loss of motor function in the lower extremities occurring intra- or postoperatively and persisting >1 month.
Procedural Blood Loss \geq 1000 cc	A blood loss \geq 1000 cc occurring before the subject leaves the operating room.
Renal Failure	Failure of renal function requiring dialysis.
Respiratory Failure	Need for mechanical ventilation for > 24 hours postoperatively, or re-intubation for any reason.
Stroke	Development of a new neurological deficit that persists > 24 hours, or worsening of previous neurological symptoms that persist > 24 hours and classified as stroke by a physician.

Secondary Endpoints:	Definition
Aneurysm-Related Mortality	
Aneurysm-related mortality is defined as death from rupture of the abdominal aortic aneurysm or from any initial or secondary procedure intended to treat the AAA. If a death occurred within 30 days of any procedures intended to treat the AAA, then it is presumed to be aneurysm-related unless there is evidence to the contrary. Deaths that occurred after 30 days of any procedures intended to treat the AAA that are procedure-related should be aneurysm-related.
 
Ultimate adjudication of relatedness of death will be made by the Clinical Events Committee (CEC). Excluded are aneurysms in anatomic areas other than the targeted segment treated by the Endurant Evo AAA stent graft system.

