Stent Graft Migration	
Stent graft migration can be attributed to migration of the main body stent graft or migration of a stent graft limb/extension.
 
Main body stent graft migration is defined as evidence of movement of the main body stent graft relative to fixed anatomic landmarks, which is not due to remodeling of the subject's vasculature. Proximal migration is observed when the stent graft completely covers a renal artery or movement is > 10 mm. Distal migration is observed when the stent graft moves > 10 mm distally relative to fixed anatomic landmarks.
 
Stent graft limb/extension migration is defined as evidence of movement of the stent graft limbs/extensions relative to fixed anatomic landmarks, which is not due to remodeling of the subject's vasculature. Proximal migration is observed when the distal part of the stent graft limb/extension moves > 10 mm proximally. Distal migration is observed when the distal part of the stent graft limb/extension moves > 10 mm distally or completely covers the internal iliac artery.

Secondary Procedures	A secondary procedure is defined as any endovascular or surgical

	
procedure performed following the completion of the operative initial implantation procedure (thus on subsequent occasion after final closure of the last artery access site) which involves the targeted vascular segment treated by the Endurant Evo AAA stent graft system, including access sites and bypasses of the targeted vascular segment in which there is either manipulation of the implanted Endurant Evo stent graft or implantation of any additional devices. (Procedures related to complications due to the use of a closure device are excluded from this definition)

Aneurysm Expansion	
Aneurysm maximum diameter increase >5 mm as compared to the 1- month contrast enhanced imaging measurements

Aneurysm Rupture	
Rupture or perforation of the targeted abdominal aneurysmal sac as detected by angiography, CT scan, and/or direct observation at surgery or autopsy.
 
Aneurysm rupture should be reported as either procedure-related aneurysm rupture, (i.e., perforation of the aneurysm during the course of the implantation procedure), or as a late aneurysm rupture that follows device deployment.
 
Excluded are aneurysms in anatomic areas other than the targeted segment treated by the Endurant Evo AAA Stent graft system.

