Conversion to Open Surgery	
Conversion of the endovascular procedure to an open procedure required at the time of the index procedure (primary conversion) or at a time beyond the initial endovascular procedure (secondary conversion).

Major Adverse Events	
Major Adverse Events include the occurrence of any of the following:
 
 • All-cause Mortality • Bowel Ischemia • Myocardial Infarction • Paraplegia • Procedural Blood Loss \geq1000 cc • Renal Failure • Respiratory Failure • Stroke
Stent Graft Occlusion	
Defined as a 100% blockage of the lumen diameter of any implanted the stent graft component(s) as evidenced by CT, angiography, ultrasound, or other appropriate imaging modality, and/or operative or pathological analysis.

Endoleak	
Defined by the presence of contrast-enhanced blood outside the lumen of the endoluminal graft but within the aneurysm sac.
 
Type I - Endoleak resulting from an incomplete seal of the endograft proximally or distally; the endoleak is in continuity with the proximal anchoring site (proximal endoleak) or the distal anchoring site (distal endoleak) of the device reaching the aneurysm sac.
 
 Type I a - Leak at the proximal graft attachment site Type I b - Leak at the distal graft attachment site. Type I c - Leak around an occluding plug 
Type II - Endoleak resulting from a collateral vessel entering the aneurysmal sac resulting in retrograde filling (e.g. inferior mesenteric, middle sacral, hypogastric, accessory renal or lumbar arteries).
 
Type III - Endoleak resulting from a defect of fabric or between the segments of the modular graft (junctional endoleak).
 
 Type III a – Endoleak between the segments of the modular

	
graft (junctional endoleak).
 
Type III b – Endoleak in the mid-graft region due to the defect of fabric
 
Type IV – Transgraft leak due to fabric porosity within 30 days after index procedure.
 
Type V – Aneurysm enlargement in the absence of any demonstrable perfusion of the aneurysmal sac.
 
Type undetermined – Endoleak of undefined origin

--	--

Device Deficiency	Definition
Anchoring Pin Fracture	Fracture or breakage of the anchoring pin.
Anchoring Pin Detachment From Aorta	Detachment of the anchoring pin that secures the stent graft to the aorta.
Suprarenal Bare Stent Fracture	Fracture or breakage of the suprarenal bare stent.

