3.2. Sample Size Consideration

A sample of 40 subjects will be treated and analyzed to support regulatory approval. The sample size of 40 subjects is considered adequate to assess the primary safety endpoint, which is defined as the proportion of subjects experiencing a MAE within 30 days post-implantation.

Considering the reported MAE rate from the ENGAGE Post-Approval Study (PAS), which evaluated the long-term safety and effectiveness of the Endurant Stent graft system in 328 subjects¹, it is estimated that 2 of 40 (5%) subjects treated with Endurant Evo AAA stent graft system will experience a MAE. The precision of this assumed 5% point estimate can be assessed by calculating the difference from the 1-sided 95% upper confidence limit. This difference, or margin of error, is calculated to be < 10% for the Endurant Evo International Clinical Trial and is therefore considered adequate to assess the primary safety endpoint^{2,3}.

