8.1. General consideration

All endpoints will be analyzed descriptively. In general, qualitative parameters will be described by their distribution frequencies; quantitative parameters will be described by their mean, standard deviation, minimum, maximum, median, and number of subjects with assessable data.

The survival from all-cause mortality over one year time or longer will be described by the Kaplan-Meier survival curve and the associated Kaplan-Meier estimate will be calculated along with its standard error using the Greenwood method.

For events such as AEs, deaths and secondary procedures, that can occur or are observed at any time during the study, no time window will be applied. For such events, an event that occurs “within 1 month or 30 days” is an event that takes place between Days 0 to 30, inclusive.

Similarly, an event that occurs “within 12 months or 365 days” is an event occurring between Day 0 to Day 365, inclusive. Date of event onset will be used to determine when the event occurred. Day 0 is referring to the day of index procedure.

For image-based assessments, such as stent-graft endoleak, patency, and other observations, the following time windows will be applied for by-visit data summaries:

Table 1: Time Windows for Statistical Analyses

Study Visit	Target Day	Time Window
Implant	Day 0	Day 0
1 Month	Day 30	1 – 90 days
6 Months	Day 183	91 – 304 days
12 Months	Day 365	305 – 548 days
2 Year	Day 731	549 – 913 days
3 Year	Day 1096	914 – 1278 days
4 Year	Day 1461	1279 – 1644 days
5 Year	Day 1826	1645 – 2009 days

If different type of images are used but have different finding in the same time window, the imaging technique and sensitivity matrix (Appendix 12.1) will be applied. Finding from higher visibility image will be used for analysis. If there are two or more assessments from the same type of image in the same time window, then the assessment closest to the target day will be used in the analysis of event rate at a given time point.

Statistical analyses for this study will be performed using the Statistical Analysis System (SAS) for Windows (Version 9.1 or higher) or other widely-accepted statistical or graphical software.

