$n = \text{No. of Subjects Who Had Readable Images}$	No. of subjects who had a readable image within the 1-month window.	No. of subjects who had a readable image within the 6-month window.	No. of subjects who had a readable image within the 12-month window.
Event rate = m/n	Through 1 Month	Through 6 Months	Through 12 Months
$m = \text{No. of Subjects Who Had Event(s)}$	No. of subjects who had an event with scan day within the 1-month window.	No. of subjects who had an event with scan day within 1- or 6-month windows.	No. of subjects who had an event with scan day within 1-, 6- or 12-month windows.
$n = \text{No. of Subjects Who Had Readable Images}$	No. of subjects who had a readable image within the 1-month window.	No. of subjects who had an event (counted in m) or had a readable image	No. of subjects who had an event (counted in m) or had a readable image

		within the 6-month window.	within the 12-month window.
--	--	----------------------------	-----------------------------

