8.5. Analysis of the Secondary Endpoints

Descriptive statistical analyses will be performed on secondary endpoints. No inferential statistical analysis is planned for secondary endpoints.

Event rates such as mortality, secondary procedures, serious adverse events, conversion to open surgery, and aneurysm ruptures will be calculated in the same way as the MAE rate, specified in Table 2.

The survival from all-cause and aneurysm-related mortality over one year time or longer will be presented with the Kaplan-Meier survival curve and the associated Kaplan-Meier estimate will be calculated along with its standard error using the Greenwood method.

Imaging based event rate such as stent graft migration, aneurysm expansion, endoleaks, stent graft occlusions, and device deficiencies will be calculated in the way as specified in Table 3.

9. Additional Data Summaries / Supplemental Analyses

Descriptive data summaries will be provided for acute procedural observations and clinical utility measures.

10. Data Screening and Acceptance

Data management will be done according to Medtronic SOPs and the Data Management Plan for this clinical study. These documents will be made available upon request.

All collected data will be reviewed for completeness, correctness and consistency. In case of issues, queries will be sent to the investigator or designee to complete, correct or comment the data.

11. List of Planned Tables, Listings, and Figures

List of planned tables, listing, and figures for the analyses can be found in a separate table shell document.

12. Appendices

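### SAP Table 2 reports interval counts as 'within 183 days' and 'within 365 days' rates, contradicting the Day 0 rule in SAP 8.1 and protocol H.1

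*SAP*

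**What the plan says.** SAP 8.1 and protocol H.1 carry the same rule for events that can occur at any time. Within 30 days means Day 0 to Day 30, and an event within 365 days "is an event occurring between Day 0 to Day 365, inclusive". SAP section 5 and protocol C.2.2 list seven secondary endpoints at 30, 183 and 365 days, and MAEs at 183 and 365 days.

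SAP 8.4, Table 2, sets the rate as m/(m + k). The 30-day column counts onsets on Day 0 to 30. The column headed 'Within 183 Days' counts onsets on Day 31 to 183 only. For 'Within 365 Days', m is "No. of subjects who had at least one MAE with onset day from Day 184 to Day 365, inclusive". The event-free count k takes subjects without an MAE who have been in the study at least 1, 91 or 305 days; it does not say over what period 'without an MAE' applies.

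SAP 8.5 says that mortality, secondary procedures, serious adverse events, conversion and rupture "will be calculated in the same way as the MAE rate, specified in Table 2". Table 3, for imaging events, has a separate cumulative block; its 'Through 12 Months' numerator is "No. of subjects who had an event with scan day within 1-, 6- or 12-month windows".

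**The concern.** The general rule and Table 2 cannot both be followed for the later horizons. If Table 2 is programmed as written, interval rates appear under a cumulative label, and the endpoints named in the protocol are not calculated.

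Some events can never reach the later numerators because they happen only on Day 0. Procedural blood loss is defined in protocol L.2 as "occurring before the subject leaves the operating room". Procedure-related rupture is "perforation of the aneurysm during the course of the implantation procedure". Primary conversion belongs to the index procedure, and under protocol F.2.1.2 that subject exits at 1 month, so falls in neither m nor k afterwards. The same is true of an early death.

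In a trial with no hypothesis test, the reported rates are the result. These are 6- and 12-month safety rates for a device whose protocol (J.3) already acknowledges higher risks than other commercially available devices.

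**Working it through.** **The plan's own figure.** SAP 3.2 assumes that "it is estimated that 2 of 40 (5%) subjects treated with Endurant Evo AAA stent graft system will experience a MAE", with a margin below 10% to the one-sided 95% upper limit. The exact binomial limit for 2/40 is 14.92%, so the margin is 14.92 − 5.00 = 9.92 points. The figure reproduces, and does not depend on Table 2's later columns.

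**Scope.** Seven endpoints at 30/183/365 days plus MAE at 183/365 days make 8 endpoints × 2 later horizons = 16 rates. SAP 8.5 plans Kaplan-Meier estimates for all-cause and aneurysm-related mortality, which covers 2 × 2 = 4. The other 12 have no other cumulative figure in the SAP.

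**Formulas.** Let a, b, c be the numbers of subjects with a first event on Day 0–30, 31–183 and 184–365. Take N = 40 and, unless stated, full follow-up, no recurrence and no first event after Day 365.

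- Day 0 rule: (a + b)/N at 183 days; (a + b + c)/N at 365 days.
- Table 2, 'without an MAE' read as none since Day 0 up to the horizon: b/(N − a); c/(N − a − b).
- Table 2, read as none in the whole follow-up: b/(N − a − c); c/(N − a − b).
- Table 2, read as none in that interval: b/N; c/N.

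Only the 2 early MAEs in the first row come from the SAP; all other counts are assumed.

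| Case | Horizon | Table 2 | Day 0 rule |
|---|---|---|---|
| First events 2/0/0 | 183 and 365 | 0/38 or 0/40 = 0% | 2/40 = 5.0% |
| First events 2/1/1 | 183 | 1/37, 1/38 or 1/40 = 2.5–2.7% | 3/40 = 7.5% |
| First events 2/1/1 | 365 | 1/37 or 1/40 = 2.5–2.7% | 4/40 = 10.0% |
| 2/1/1, one early subject recurs on Day 184–365 | 365 | 2/38 or 2/40 = 5.0–5.3% | 4/40 = 10.0% |
| One primary conversion, exit at 1 month | 183 and 365 | 0/39 = 0% | 1/40 = 2.5% |
| One death on Day 10 | 183 and 365 | 0/39 = 0% | 1/40 = 2.5% |
| One Day 0 blood loss ≥1000 cc, no other MAE | 183 and 365 | 0/39 or 0/40 = 0% | 1/40 = 2.5% |
| Two early subjects both recur on Day 184–365, plus one new | 365 | 3/40 = 7.5% | 3/40 = 7.5% |
| First events 0/0/2 | 365 | 2/40 = 5.0% | 2/40 = 5.0% |

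In the first row Table 2 reads 5.0%, 0%, 0% across 30, 183 and 365 days. A cumulative proportion with complete follow-up cannot fall. The last two rows show that some patterns give no error at 365 days.

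With all 69 enrolled subjects, 2/1/1 at 365 days gives 1/66 or 1/69 = 1.4–1.5% under Table 2, against 4/69 = 5.8%.

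**The case against.** **Interval rates may have been intended.** The three intervals are disjoint and contiguous, early events stay visible in the 30-day column, and for once-only events such as death the interval numerators can be added up. That arithmetic stands. However, neither document mentions interval endpoints. The 91- and 305-day thresholds in k are the opening days of the 6- and 12-month windows in SAP Table 1, not the start of risk at Day 31 or 184. For MAEs, serious adverse events and secondary procedures, adding the numerators can count one subject twice. If intervals were meant, the headings are wrong and the protocol's endpoints are missing, so a correction is needed either way.

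**Little rests on these rates.** They are descriptive, with no decision rule, and the regulatory analysis is triggered at 30 days of follow-up in 40 subjects, when the later columns would be largely immature. This stands, and it limits the consequence. It does not settle which of two contradictory definitions a programmer should use for later reports.

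**The 183-day conflict is less explicit.** The Day 0 rule is spelled out only for 30 and 365 days. For 183 days it follows by analogy and from the endpoint wording. That is correct, and the 365-day contradiction needs no such inference.

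**The shells may differ.** The table shells are a separate document, not seen here. They could carry the right labels, but Table 2 would still contradict SAP 8.1.

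**Conclusion.** The concern holds. Table 2's two later columns contradict SAP 8.1 and protocol H.1 and depart from the cumulative pattern of Table 3. Sixteen secondary rates are affected, 12 of them without any other cumulative estimate.

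In the cases above the 365-day understatement is 0 to 7.5 points (largest: 10.0% reported as 2.5%). That span illustrates rather than bounds, because it rests on assumed event timing, N = 40 and mostly complete follow-up. For Day 0 events, early deaths and primary conversions the omission does not depend on how k is read.

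The 30-day primary safety rate, technical success and the sample-size margin stand as planned.

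**What to change.** - In Table 2, define m as subjects with at least one event with onset on Day 0–183 and on Day 0–365.
- State that 'without an MAE' in k means none from Day 0 to that horizon.
- State in SAP 8.5 that the same rule holds for the other event endpoints.
- If interval counts are wanted, keep them as extra columns labelled Day 31–183 and Day 184–365.
- Keep the 91- and 305-day thresholds in k unless the sponsor changes them explicitly. They have a side effect to note: subjects with an event count whenever they exit, but event-free subjects who exit early do not. With 4 events and 4 event-free exits before Day 305 among 40 subjects, the rate is 4/36 = 11.1%, against 4/40 = 10.0% of all enrolled.

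The cost is wording in Table 2 and SAP 8.5, plus any matching shells; no new data. Most reported rates will stay the same or rise. If 'without an MAE' had been read over the whole follow-up, a rate can fall slightly: first events 0/1/3 take the 183-day rate from 1/37 = 2.7% to 1/40 = 2.5%. The same shift occurs at 365 days with one event on Day 184–365 and three first events after Day 365.
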